
## 4 STUDY SCHEMATIC

## 5 SCHEDULE OF ASSESSMENTS

*Table 1 Schedule of Assessments*

Assessments	-3 to - 1 	Study Days													Day 42 Safety F/U 	
		1	2	3	4	5	6	7	8	9	10	11	12	13	14	
ICF signed	X															
Inclusion/exclusion criteria	X	X														
Demographics; medical and surgical history	X	X														
Review concomitant medication(s) 	X	X	X	X	X	X	X	X	X	X	X	X	X	X 	X	X
Review of adverse events 		X	X	X	X	X	X	X	X	X	X	X	X	X 	X	X
Physical examination 	X	X	X	X	X	X	X	X	X	X	X	X	X	X	X	X
WHO questionnaire 	X	X	X	X	X	X	X	X	X	X	X	X	X	X 	X	X
Vital signs 	X	X	X	X	X	X	X	X	X	X	X	X	X	X	X	X
Oxygen flow (L/min) 	X	X	X	X	X	X	X	X	X	X	X	X	X	X 	X	X
Height and Weight 	X															
HbA1c	X															
Pharyngeal viral sample 	X	X			X			X			X			X	X	X
12-lead ECG 	X	X														
Chest X-ray or CT scan 	X															
Serum chemistry 	X	X			X			X			X			X		
Hematology (CBC with differential) 	X	X			X			X			X			X		

Assessments	-3 to - 1 	Study Days													Safety F/U 	
		1	2	3	4	5	6	7	8	9	10	11	12	13	14	
D-dimer, cardiac troponin, CRP, LDH, ferritin 	X							X							X	
Urinalysis	X															
Serum or urine pregnancy test 	X															

 Protocol defined End of Treatment (EOT) occurs on Day 14. For subjects discharged from the hospital prior to Day 14, these assessments will be performed on a daily basis after discharge, via phone until Day 14.

 daily assessments whilst patient is hospitalized; vital signs = temperature, blood pressure, pulse rate, respiratory rate and oxygen saturation by pulse oximeter and recording of supplemental oxygen requirement as oxygen flow (L/min) and FiO2 estimate; special attention to the possibility of neuropsychiatric (e.g. anxiety, agitation, insomnia), and cardiopulmonary abnormalities (e.g. tachycardia, palpitations, chest pain, syncope)

 For WHO questionnaire (WHO ordinal scale for clinical improvement) -refer to Appendix 1

 record weight if even if just by patient estimate

 In screening, pharyngeal samples for SARS-CoV-2 PCR to be collected up to 7 days prior to screening. During treatment, samples are collected every 3 days $\pm$ 1 day, other than a confirmatory negative swab at least 24 hours after the first and a Day 14 swab if not confirmed negative prior. Once two confirmed negative swabs are obtained, no further testing need be done. For patients having nasopharyngeal swabs, the same nostril must be used during the study. In countries where regulatory guidelines do not require a negative swab in order for a patient to be discharged from the hospital, reasonable efforts will be made to arrange for testing to be performed either at an external clinic or at the subject's home.

 Screening ECG is required. Additionally, all patients will have a 12-lead electrocardiogram prior to the first study drug administration on Day 1 and approximately 3 hours after the first dose. If patients are on monitors (including telemetry or Holter monitors), investigators are encouraged to collect QT interval data

 In screening chest X-ray or CT scan (performed up to 7 days prior to randomization). Chest X-ray or CT scan, lab draws will be at the discretion of the Investigator depending on patient clinical condition

 Every 3 days  $\pm$  1 day. Serum Chemistries will include at a minimum albumin, alkaline phosphatase, ALT, AST, bicarbonate, total bilirubin, BUN, calcium, chloride, creatinine, glucose, potassium, total protein, sodium, uric acid.

 CBC with differential once every 3 days  $\pm$  1 day

 CRP=C-reactive protein, LDH=lactate dehydrogenase, cardiac troponin (Troponin C, I or T, but must be consistent for each patient throughout the study), D-dimer, ferritin, once weekly  $\pm$ 2 days

 women of childbearing potential; serum or urine pregnancy test must be negative within 3 days prior to randomization

 The Day 42 follow-up visit should be performed wherever possible but

may be performed by telephone if returning to the hospital site is not feasible per Investigator and/or patient decision. Only AEs, WHO questionnaire, concomitant medications and oxygen flow will be collected by telephone.

 Laboratory values and other diagnostic tests that have been obtained prior to the ICF being signed may be used if within the time allotted for the screening period.

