Statistical Methods	
The primary efficacy endpoint will be based on a success (Yes/No) variable, indicating if a subject is no longer requiring supplemental oxygen, for at least 24 hours by study Day 14 (patient death or subsequent requirement of supplemental oxygen or lost to follow-up through Day 42 will be regarded as failure for the primary efficacy endpoint). Any subject reported as not requiring supplemental oxygen on any given study day will be counted as a subject who has not required oxygen for at least 24 hours, based on the instructions to sites to enter the highest oxygen requirement for each study day. Subjects who are discharged from hospital on supplemental oxygen are expected to be followed up by the study site daily and will be considered a success only if for any given study day, the highest supplemental oxygen requirement is zero. By definition, death before day 14 will be regarded as a failure, even if prior room air has been achieved. If a patient initiates a new investigational therapy on a different formal clinical protocol for COVID-19 within 14 days of randomization, the patient will be followed for true outcomes in the primary analysis but be censored at the time that the new therapy was initiated in a sensitivity analysis.
 
If a subject discontinues the study prematurely before reaching success, prior to Day 14, they will be counted as a failure for the primary analysis. Sensitivity analysis using time to event method will be performed censoring these cases at the latest informative time.
 
The number and percentages of subjects achieving success (as defined above) will be tabulated per treatment group. A 95% confidence interval will be constructed for each proportion. A Cochran Mantel-Haenzel (CMH) test will compare the proportion of success between the two groups, using the study stratification factors used for randomization, and a corresponding stratified risk difference estimate will be presented with 95% confidence interval.
 
The significance level for this test will be two-sided 5%. The primary analysis will be based on the modified Intent to treat population (mITT analysis set) which consists of all patients that were randomized and treated with at least one dose of study drug and who met entry criteria #3 (The patient requires, at baseline, high flow supplemental oxygen or positive pressure ventilation, or is receiving oxygen via non-rebreather mask or reservoir mask, capable of delivering high concentrations of oxygen. Patients who require mechanical ventilation or no longer require supplemental oxygen prior to receiving the first dose of study drug will not be included in the mITT analysis set.

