#### **14.1.3 The following will be monitored and documented daily for discharged subjects (as collected from follow-up phone calls) or for subjects having terminated treatment early and who are continuing in the study**

- WHO Ordinal Scale for Clinical Improvement level
- Concomitant medications
- Adverse Events, including specific assessment for signs of neuropsychiatric (e.g. anxiety, agitation, insomnia), and cardiopulmonary abnormalities (e.g. tachycardia, palpitations, chest pain, syncope)
- Oxygen requirement (L/min)
- In countries where regulatory guidelines do not require a negative swab in order for a patient to be discharged from the hospital, reasonable efforts will be made to arrange for testing to be performed either at an external clinic or at the subject's home.

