#### **14.1.5 Safety Follow-up (Day 42)**

##### Day 42

- Concomitant medications
- Adverse Events
- WHO Ordinal Scale for Clinical Improvement level
- Physical exam, specifically assessing neuropsychiatric and cardiopulmonary abnormalities
- Oxygen requirement (L/min)

The follow-up visits may be performed by telephone if returning to the hospital site is not feasible per Investigator and/or patient decision. On Day 42, only AEs (including specific assessment for signs of neuropsychiatric (e.g. anxiety, agitation, insomnia), and cardiopulmonary abnormalities (e.g. tachycardia, palpitations, chest pain, syncope), WHO questionnaire, concomitant medications and oxygen flow will be collected by telephone.

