### 15.2 Secondary

- 1) The percentage of patients with  $\geq 2$  category improvement on the WHO Ordinal Scale for Clinical Improvement by Day 14 for the opaganib arm as compared to the placebo arm
- 2) Time to recovery as defined by improvement to a score of 3 or less on the WHO Ordinal Scale for Clinical Improvement for the opaganib arm as compared to the placebo arm
- 3) Time to low oxygen flow via nasal cannula e.g. from high oxygen flow via nasal cannula or positive pressure ventilation at baseline
- 4) The time to discharge from the hospital for the opaganib arm as compared to the placebo arm
- 5) The percentage of patients requiring intubation and mechanical ventilation by day 42 for the opaganib arm as compared to the placebo arm
- 6) The time to two consecutive negative swabs for SARS-CoV-2 by PCR, at least 24 hours apart for the opaganib arm as compared to the placebo arm
- 7) The percentage of patients with at least two consecutive negative swabs for SARS-CoV-2 by PCR at Day 14 for the opaganib arm as compared to the placebo arm
- 8) The percentage of patients with at least one measurement of fever at baseline (defined as temperature  $>38.0$  C [100.4 F]), who are afebrile (defined as temperature  $<37.2$  C [99 F]) at Day 14 for the opaganib arm as compared to the placebo arm
- 9) Mortality due to any cause at Days 28 and 42 after baseline for the opaganib arm as compared to the placebo arm

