## 19.4 Analysis of the Primary Efficacy Endpoint

The primary efficacy endpoint will be based on a success (Yes/No) variable, indicating if a subject is no longer requiring supplemental oxygen, for at least 24 hours by study Day 14 (patient death or subsequent requirement of supplemental oxygen or lost to follow-up through Day 42 will be regarded as a failure for the primary efficacy endpoint). Any subject reported as not requiring supplemental oxygen on any given study day will be counted as a subject who has not required oxygen for at least 24 hours, based on the instructions to sites to enter the highest oxygen requirement for each study day. Subjects who are discharged from hospital on supplemental oxygen are expected to be followed up by the study site daily and will be considered a success only if for any given study day, the highest supplemental oxygen requirement is zero.

If a patient initiates a new investigational therapy on a different formal clinical protocol for COVID-19 within 14 days of randomization, the patient will be followed for true outcomes in the primary analysis but in a sensitivity analysis the data under the new therapy will not be included.

An early discontinuation of study before the subject has reached success (e.g. loss to follow up) thus preventing continued follow-up for success by Day 14, will be considered as missing data and will be counted as failure for the primary analysis. Sensitivity analysis using time to event method will be performed censoring these cases at the latest informative time.

The number and percentages of subjects achieving success (as defined above) will be tabulated per treatment group. A 95% confidence interval will be constructed for each proportion. A Cochran Mantel-Haenzel (CMH) test will compare the proportion of success between the two groups, using the study stratification factors used for randomization, and a corresponding stratified risk difference estimate will be presented with 95% confidence interval.

The significance level for this test will be two-sided 5%.

The primary analysis will be based on the modified Intent to treat population (mITT) as defined in Section 19.3.

Sensitivity and supportive analyses for the primary endpoint analysis will be defined and detailed in the statistical analysis plan. These will address at least the following aspects:

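### Renewed oxygen up to Day 42 undoes a primary success, but patients discharged on room air have no clearly scheduled oxygen record on Days 15 to 41

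*Protocol*

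**What the plan says.** **The rule.** Section 19.4 states that "patient death or subsequent requirement of supplemental oxygen or lost to follow-up through Day 42 will be regarded as a failure". The synopsis agrees: "subsequent requirement of supplemental oxygen or lost to follow-up through Day 42 will be regarded as failure for the primary efficacy endpoint". Section 19.4 also rests success on sites entering the highest oxygen need for each study day, so the endpoint is built on a daily record.

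**The schedule.** Table 1 (section 5) passes from Day 14 to Day 42 with no column between.
- Footnote 1, for patients discharged before Day 14: "these assessments will be performed on a daily basis after discharge, via phone until Day 14".
- Footnote 2: "daily assessments whilst patient is hospitalized", with no end day. Section 14.1.2 likewise sets no end day for inpatients.
- Section 14.1.3: "The following will be monitored and documented daily for discharged subjects (as collected from follow-up phone calls". Again there is no end day.
- Section 19.4 expects daily follow-up of patients discharged on oxygen, also with no end day.

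**Day 42.** Section 14.1.5 lists "Oxygen requirement (L/min" among its items, and the synopsis asks for type and flow. Footnote 12 limits a telephone contact: "Only AEs, WHO questionnaire, concomitant medications and oxygen flow will be collected by telephone". None of these asks about oxygen need since Day 14.

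**Other routes.** Section 13.1.2 names supplemental oxygen as a supportive therapy, and section 13.1.3 requires supportive therapy to be recorded from Day 1 to the final follow-up visit. Section 17.6 sets the adverse event window, and section 17.6.3 makes a sudden, important rise in oxygen need reportable. Section 19.4 plans a sensitivity analysis that ignores events after Day 14.

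**The concern.** The failure window of the primary endpoint runs four weeks past the point at which footnote 1 stops the daily record after discharge. A patient still in hospital can be read as observed every day to Day 42. A patient at home on room air is asked about oxygen on Day 42, and the item is not worded to cover the interval. The same relapse, for example a few days of oxygen around Day 20, would be seen in the first patient and might not be seen in the second.

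Time to discharge is secondary endpoint 4, so discharge status is an outcome that treatment is hoped to change. If ascertainment depends on it, the arms can differ in how often relapse is detected as well as in how often it occurs. An analysis plan cannot repair this later, because it cannot recover data that were not collected.

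**Working it through.** **1. Who has a scheduled oxygen record on Days 15 to 41 (41 - 15 + 1 = 27 days)?**

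| Patient | Governing text | Daily record after Day 14? |
|---|---|---|
| Still in hospital | Footnote 2; section 14.1.2 | Yes, on a plain reading; no end day |
| Discharged on oxygen | Section 19.4; section 14.1.3 | Implied; no end day |
| Discharged on room air before Day 14 | Footnote 1 against section 14.1.3 | Contradictory: footnote 1 stops at Day 14, section 14.1.3 does not stop |
| Discharged on room air after Day 14 | Section 14.1.3 only; no column in Table 1 | Unclear |

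**2. What else would catch a relapse at home?**
- *Supportive-therapy recording (sections 13.1.2 and 13.1.3).* Oxygen given on Day 20 should be entered. The protocol does not tie this record to the primary endpoint, and after discharge it depends on what the patient volunteers at Day 42.
- *Adverse events (section 17.6).* The minimum period is 28 days after study drug stops. That reaches Day 42 for a patient treated to Day 14 (14 + 28 = 42), but only Day 33 for one who stops on Day 5 (5 + 28 = 33).
- *Special-interest reports (section 17.6.3).* These are at the investigator's discretion and need the site to know of the event.
- *Readmission.* This meets the definition of a serious adverse event and should surface. Short oxygen episodes at home are the likeliest misses.

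**3. The plan's own figure.** Inputs from section 19.1: 40% versus 55%, two-sided alpha 0.05, 90% power, chi-square test, 1:1 allocation. With pooled variance and no continuity correction:

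n per arm = [1.960 × √(2 × 0.475 × 0.525) + 1.282 × √(0.40 × 0.60 + 0.55 × 0.45)]² / 0.15² = 231, or 462 in total.

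At 232 per arm the power is 90.1%. The stated 464 is sound and is not disputed.

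**4. Illustration of size.** The protocol gives no relapse or detection rate, so these are assumptions. Take 40% and 55% as the success rates before any relapse after Day 14 is counted. Let r be the proportion of successes who relapse and d the proportion of relapses detected, in the control (C) and opaganib (T) arms. The error in the observed difference, in percentage points, is

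error = 55 × r_T × (1 - d_T) - 40 × r_C × (1 - d_C).

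With no relapse detected (d = 0), the observed difference stays at 15.0 points:

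| Relapse, control / opaganib | Rates if all counted | Correct difference | Error |
|---|---|---|---|
| 2% / 2% | 39.2% / 53.9% | 14.7 | +0.3 |
| 5% / 5% | 38.0% / 52.25% | 14.25 | +0.75 |
| 10% / 10% | 36.0% / 49.5% | 13.5 | +1.5 |
| 5% / 10% | 38.0% / 49.5% | 11.5 | +3.5 |
| 10% / 5% | 36.0% / 52.25% | 16.25 | -1.25 |

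Zero detection is the extreme case. If half are detected in both arms, each error halves. At 10% relapse with 232 per arm, the relapses number about 9.3 (control) and 12.8 (opaganib).

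**The case against.** The strongest reply is that the protocol already has several ways to learn of a relapse. Inpatients are recorded daily. Section 14.1.3, read alone, continues daily calls after discharge. Sections 13.1.2 and 13.1.3 together oblige sites to record oxygen through the final visit, and section 18.1.6 requires dated source notes for concomitant medication. Adverse event and special-interest reporting add further routes. The sensitivity analysis that ignores events after Day 14 will show whether the conclusion depends on them. The eCRF and the site instructions are not shown and may already date oxygen use over the interval.

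Much of this stands, and it rules out several stronger readings that a reader might infer:
- *That nothing is assessed on Days 15 to 41.* Footnote 2 and sections 14.1.2 and 14.1.3 say otherwise for at least some patients.
- *That Day 42 records only oxygen at that moment.* Adverse events and concomitant medications are collected too.
- *That most relapses go unseen.* One could argue that a 7-day episode with uniform onset over 28 days is visible at a single look with probability 7/28 = 25%. That treats the Day 42 flow reading as the only route, which the protocol contradicts.
- *That secondary endpoint 5 ("The percentage of patients requiring intubation and mechanical ventilation by day 42") rests on serious adverse event reports alone.* An intubated patient is an inpatient with a daily WHO level, and decline leading to intubation is a special-interest event.
- *That the bias favours opaganib.* The last row of the table shows it can go the other way.

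The reply does not remove the mismatch. The routes for a patient at home are indirect, are not named as sources for the primary endpoint, and lean on unprompted recall. The sensitivity analysis leaves the primary analysis as it is.

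**Conclusion.** The point holds as a mismatch between endpoint and schedule. The primary failure rule runs to Day 42, while for patients discharged on room air footnote 1 ends the daily oxygen record at Day 14, section 14.1.3 contradicts it, and the Day 42 item does not look back. One failure condition is therefore ascertained differently by discharge status.

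Neither the size nor the direction of any bias can be set from the documents. The illustrative errors, +0.3 to +1.5 points for equal relapse and about -1.3 to +3.5 points for 5% versus 10%, set against a planned 15, assume that every relapse is missed and that 40% and 55% are rates before later relapse is netted out. Section 19.1 states those rates at 14 days and does not say which is meant. The correction is worth making because it is cheap and the data cannot be reconstructed afterwards.

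**What to change.** 1. Add to the Day 42 contact (Table 1, footnote 12 and section 14.1.5) one look-back item: any supplemental oxygen, readmission or intubation since Day 14, with start and stop dates. Telephone is sufficient.
2. Reconcile footnote 1 with sections 14.1.2, 14.1.3 and 19.4, so that one rule says when daily oxygen recording ends for inpatients, for patients discharged on oxygen and for patients discharged on room air.
3. State in section 19.4 that the part of the primary endpoint after Day 14 is derived, in all patients, from these dated records together with the supportive-therapy page.

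The cost is one eCRF item at an existing contact and some wording changes, with no extra visit. The downside is recall error over four weeks, but a direct, dated question should suffer less from it than the unprompted recall the plan now relies on.

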## 6 LIST OF ABBREVIATIONS

Abbreviation	Definition
ADE	Adverse Device Effect
AE	Adverse Event
ALT (SGPT)	Alanine aminotransferase (serum glutamic pyruvate transaminase)
ARDS	Adult Respiratory Distress Syndrome
AST (SGOT)	Aspartate aminotransferase (serum glutamic oxaloacetic transaminase)
AUC	Area under the curve
COVID-19	Coronavirus Disease of 2019
CFR	Code of Federal Regulations
CRO	Clinical Research Organization
CYP	Cytochrome P450
DSMB	Data Safety Monitoring Board
EC	Ethics Committee
ECG	Electrocardiogram
eCRF	Electronic Case Report Form
EOT	End of Treatment
FDA	United States Food and Drug Administration
FiO2	Fraction of Inspired Oxygen
GCP	Good Clinical Practice
HBEC	Human bronchial epithelial cells
IB	Investigator Brochure
ICH	International Conference on Harmonisation
IND	Investigational New Drug
IRB	Institutional Review Board
MedDRA	Medical Dictionary for Regulatory Activities
NCI-CTCAE	NCI Common Terminology Criteria for Adverse Events
NG	Nasogastric
PCR	Polymerase Chain Reaction
QTc	Corrected QT
QTcF	Corrected QT using Friedericia's formula
RTC	Replication transcription complex
S1P	Sphingosine-1-phosphate
SARS-CoV-2	Severe acute respiratory syndrome coronavirus 2

SAP	Statistical Analysis Plan
SAE	Serious adverse event
SK2	Sphingosine kinase 2
SUSAR	Suspected unexpected serious adverse reaction
TEAE	Treatment Emergent Adverse Event
ULN	Upper limit of the normal range
WHO	World Health Organization
WOCBP	Women of Childbearing Potential

## 7 BACKGROUND INFORMATION

### 7.1 COVID-19 Disease

COVID-19 is a newly recognized disease caused by a coronavirus virus, SARS-CoV-2. A flu-like illness was first noted in December 2019, in Wuhan, China and was subsequently attributed to a virus similar to the SARS coronavirus, which is now designated as SARS-CoV-2. While the clinical spectrum has not yet been well defined, early reports suggest that SAR-CoV-2 infection ranges from asymptomatic infection to pneumonia and Adult Respiratory Distress Syndrome (ARDS) with multiorgan failure that may lead to death (Zhou, 2020). In the Zhou study, the median duration of viral shedding was 20 days, with an interquartile range of 17-24 days and a maximum of 37 days. Common symptoms reported in the Zhou study for 191 patients were fever (94%), cough (79%), sputum production and fatigue (each 23%) and myalgia (15%). Bilateral pulmonary infiltrates were noted in 75% of patients on chest X-ray. Patients over 65 years and those with significant comorbidities, such as diabetes, cardiac or pulmonary disease, appeared to be more susceptible for developing severe infection and had a relatively higher mortality rate compared to younger, otherwise healthy patients. The incidence of symptomatic and severe infection, as a proportion of infected patients, is not yet known, as test availability, utilizing Polymerase Chan Reaction (PCR) performed on nasopharyngeal swabs or other body fluids, has been limited.

For most individuals testing positive, COVID-19 currently appears to be self-limiting. The major threat to this viral pandemic is spread through a nonimmune population, and to those most at risk of severe infection. SAR-CoV-2 is highly contagious, with spread by aerosol and surface contact (van Doremalen, 2020) and potential fecal spread (Chen, 2020). As this is a newly identified disease, first noted in December 2019, and as testing and interpretation of data are in a very early stage, no specific therapy has demonstrated antiviral efficacy.

